**Figure 2. Syringe unmasked (left) and masked (right) with amber tinted tape**

participants with appointment cards, 3) telephoning, emailing or texting participants 1-2 days before their upcoming data collection as a reminder or immediately after any missed follow up; 4) streamlining procedures to allow participants to complete assessments quickly; and 5) keeping data collection instruments as concise as possible to avoid participant fatigue. We will request that participants provide multiple, acceptable methods for contacting them (updated, as needed, at each contact). Women who miss a rescheduled appointment will not be contacted again for the visit in case they have changed their mind about study participation.

## E. Statistical Considerations

**Analysis of Objective 1.** A noninferiority analysis will be used for the primary outcome of time to lactogenesis II. Noninferiority trials are appropriate when the goal is to show that a new treatment (immediate postpartum DMPA initiation) is not clinically worse than an active control (placebo injection, open control); this is in contrast to the standard superiority trial, in which the goal is to show that a new treatment is *better* than the control. Noninferiority will be determined based on the relationship of two-sided 95% confidence intervals (CIs) to pre-specified noninferiority margins. Noninferiority of the intervention arm over the other two arms combined will be accepted if the upper bound of a two-sided 95% CI for the mean difference between groups (intervention – placebo and open control) is less than 6 hours. Although a clinical significant delay in lactogenesis has not been well established, this difference is conservatively sensitive for a noninferiority test given that many common medical interventions (e.g., epidural anesthesia, labor induction, and Cesarean delivery) have been shown to delay lactogenesis stage II by up to 12 hours. Furthermore, the interval of 6 hours is consistent with previous research. Sensitivity analysis will evaluate excluding women in the open control arm (i.e., comparing the intervention arm to the placebo arm).

As a sensitivity analysis, we will repeat these analyses accounting for infant sex as a biological variable, as well as potential confounders including maternal factors that could affect lactogenesis: age, pre-pregnancy body mass index, primiparity, psychosocial stress, diabetes, hypertension, unscheduled Cesarean section, and intention at birth to exclusively. We also will evaluate whether the relationship of interest (e.g., immediate postpartum DMPA initiation and time to lactogenesis II) varies by maternal Black race. Finally, although we expect only a negligible amount of missing data for the primary outcome, we will assess the sensitivity of results to missing data by performing multiple imputation analyses under both missing at random and missing not at random assumptions.

For secondary outcomes (breastfeeding duration, perceived adequacy of milk production, etc.), we do not have *a priori* set noninferiority margins, and thus a traditional superiority analysis will be conducted (test for significant differences using t-tests or chi-squared tests as appropriate). We will report two-sided 95% CIs for all outcomes so that post-hoc noninferiority analyses could be conducted (i.e., to evaluate whether the CI covers a specified noninferiority margin).

**Analysis of Objective 2.** A traditional superiority analysis will be used to compare rates of use of a highly effective method of contraception (defined here as DMPA, implant, IUD, sterilization, pill, patch, or ring) at 12 months post-delivery among women in the intervention or placebo arm versus those in the open control arm. An intent-to-treat analysis will be conducted using a chi-squared test to compare the percentages of women using contraception in each group (intervention + placebo versus open control). As a sensitivity analysis, we will repeat this analysis using logistic regression in order to account for potential confounders such as maternal age, parity, gravidity, socioeconomic status, sexual activity, and prior contraceptive history. We will also repeat analyses restricting those in the intervention or placebo arm to the subset of

women who believe that they received DMPA at enrollment regardless of the accuracy of their belief as an additional sensitivity analysis. Furthermore, we will evaluate whether the relationship between immediate postpartum DMPA initiation and contraception use at 12 months differs by maternal Black race.

Given that the contraception use outcome is measured at 12 months, we anticipate some missing data; however, we have no reason to believe dropout will be differential across arms. Thus, we will assess sensitivity of results to missing data using multiple imputation analyses under both missing at random and missing not at random assumptions. The secondary outcome (DMPA use at 12 months) will be analyzed with similar methods.

**Sample size.** Sample size was based on providing high (90%) power for the primary outcome of Objective 1 (time to lactogenesis II), while also ensuring appropriate power for Objective 2. We assumed that all groups would have a mean of 65 hours with a common standard deviation of 18 hours, based on a previous study, which was consistent with past research. Setting the noninferiority margin at 6 additional hours, **with a type 1 error rate of 0.05 (two-sided 95% CI), we require 143 women randomized to each group to achieve 90% power.** As this outcome is measured very soon after randomization, we expect to have it measured on all randomized women. However, we note that even if we have a small amount of missing data for this outcome, we will still have high power. For example, if we have 10% missing data (i.e., time to lactogenesis II measured on 128 women per group), we will still have 87% power. Additionally, this sample size ensures adequate power for our sensitivity analysis comparing intervention to placebo (i.e., excluding women in the open control arm); we will have 80% power for the noninferiority analysis comparing these two groups (under the same assumptions as stated above).

The sample size justified for Objective 1 also will provide high power for Objective 2, which will be assessed using traditional superiority analyses. Based on a recent analysis of data from the National Survey of Family Growth, we assume that the rate of highly effective contraceptive use will be 50% in the open control arm. We conservatively assume a 20% attrition rate at 12 months, thus will have n=114 women in the open control arm and n=228 women in the combined injection arms (DMPA; placebo). With this sample size of randomized women, we will have 81% power to detect a contraceptive use rate of 66% in the intervention/placebo group, corresponding to a relative risk of RR=1.32.

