**Figure 1. Study design**

The study will be partially blinded: participants and study staff, including the study statistician, will be blinded as to the assignment for those in the intervention and placebo arms. In contrast, no one will be blinded as to assignment to the open control arm. (Note that it is not feasible to maintain blinding for the open control arm even among the data analysts given the planned grouping of the arms for the data analyses.) DMPA has a duration of protection of 12 weeks. Women in the intervention or placebo arm will be counseled to refrain from initiating hormonal contraception in the next 6 weeks and to refrain from initiating DMPA in the next 12 weeks. Study staff will use the "Contraceptive choice information sheet" to explain the contraceptive methods that participants can use depending on whether they are assigned to an arm that receives a shot or the arm that does not receive a shot. All participants will be counseled to use condoms post-delivery to avoid a repeat pregnancy (as they either received no shot or could have received a placebo shot). Participants will receive a supply of condoms for either 12 weeks (intervention or placebo arm) or 6 weeks (open control arm), and will be referred to receive DMPA at either 12 weeks (intervention or placebo arm) or 6 weeks post-delivery (open control arm).

Data collection, which will occur at enrollment and through 12 months of follow up, will involve 1) questionnaires on demographics, characteristics and behaviors, lactogenesis, breastfeeding and contraception use and 2) infant anthropometric measures (Table 1).

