**Screening, enrollment and randomization.** Study staff will use the "Eligibility Assessment Form" to screen pregnant and postpartum women who are recruited for the study to determine whether they meet the eligibility criteria.

If they have not already watched the recruitment video, eligible women will be given a tablet and headphones and asked to watch the video. They then will be asked to read the “Combined Consent Form” in a private location. Women will indicate their agreement to participate in the study by signing the “Combined Consent Form.” Women will be given an unsigned copy of the “Combined Consent Form” to keep for future reference, as it provides contact information for staff responsible for the conduct of the research study in the event of any questions or concerns.

If screening and signing of the “Combined Consent Form” occurs during the prenatal period, the participant will be rescreened – using the same “Eligibility Assessment Form” – after delivery before randomization. In this case, rescreening is to ensure that she meets the eligibility criteria before randomization.

Randomization will occur after delivery (ideally within 48 hours) and before hospital discharge. Stratified randomization with random permuted blocks will be generated using the randomization function within the electronic data capture system, REDCap. This process serves to conceal the allocation process by automatically revealing the arm assignment only upon study enrollment. To minimize the potential for attrition or crossover between arms, participants who are randomized to the intervention or placebo arm will be administered their assigned shot (under blinded conditions) immediately after randomization. Research pharmacy staff will ensure the correct shot is given to the correct participant by checking the randomization documentation before dispensing.

Participants will complete the “Enrollment Questionnaire” on demographics, reproductive history, attitudes and intentions on related topics including breastfeeding.

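### Cheap improvement, not an error: randomisation is stratified, but neither deciding analysis uses the strata or the prognostic factors the plan already lists, so a little precision may be left unused

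*Combined protocol and SAP*

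**What the plan says.** All references are to the combined protocol and SAP.

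- **Randomisation** (V.D, Screening, enrollment and randomization): "Stratified randomization with random permuted blocks will be generated using the randomization function" in REDCap. No stratification factor is named in the text available.
- **Objective 1 decision** (V.E, Analysis of Objective 1): "Noninferiority of the intervention arm over the other two arms combined will be accepted if the upper bound of a two-sided 95% CI" for the difference in means lies below 6 hours. No strata or covariates are stated.
- **Objective 1 covariates** (same place): "As a sensitivity analysis, we will repeat these analyses accounting for infant sex as a biological variable", together with maternal factors that include "age, pre-pregnancy body mass index, primiparity, psychosocial stress, diabetes, hypertension, unscheduled Cesarean section" and feeding intention.
- **Objective 2 decision** (V.E, Analysis of Objective 2): "An intent-to-treat analysis will be conducted using a chi-squared test to compare the percentages of women using contraception in each group". Adjustment is again a sensitivity analysis, a logistic regression for "potential confounders such as maternal age, parity, gravidity, socioeconomic status, sexual activity, and prior contraceptive history".
- **Sites** (V.B Study Population): women are recruited at OSUWMC and at Emory-affiliated hospitals. Site is in neither covariate list.

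**The concern.** When allocation is balanced within strata that predict the outcome, an analysis that ignores them leaves the between-stratum variation in the standard error. The interval is then a little wider than it need be. The same holds for strong baseline predictors kept out of the deciding model. For Objective 1 the decision rests on one confidence bound, so the width of the interval is what precision buys.

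The plan itself names factors it believes affect lactogenesis, and V.E says that common interventions, Cesarean delivery among them, delay it by up to 12 hours. Yet none of these factors bears on the decision. Without the names of the strata, a reader also cannot reproduce a stratified analysis or tell whether the adjusted sensitivity analyses contain them. Both covariate lists are worded as open-ended, so this cannot be settled from the text.

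**Working it through.** **Inputs** (V.E, Sample size, and V.A Overview): SD 18 h; equal means; margin 6 h; two-sided 95% interval; 143 women per arm, so 143 vs 286 for Objective 1. For Objective 2: 114 at 50% vs 228 at 66%.

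**1. The plan's own figures.** SE = 18 × √(1/n1 + 1/n2); power = Φ(6/SE − 1.96).

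- 143 vs 286: SE 1.844 h, half-width 1.96 × 1.844 = 3.61 h, power 90.2% (stated 90%).
- 128 vs 256: 86.8% (stated 87%).
- 143 vs 143: 80.5% (stated 80%).
- Objective 2: pooled rate (114 × 0.50 + 228 × 0.66)/342 = 0.607; SE 0.0560 under no difference and 0.0564 under the alternative; Φ((0.16 − 1.96 × 0.0560)/0.0564) = 81.3% (stated 81%).

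**2. Adjusted Objective 1.** R2 is the share of outcome variance explained by the model. The documents give none, so 0.02 to 0.10 is assumed. The variance is multiplied by (1 − R2) and, to charge for chance imbalance in seven covariates, by (N − 3)/(N − 7 − 3) = 426/419. A stratum balanced by blocks costs almost nothing.

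| Assumed R2 | Net SE (h) | Net half-width (h) | Narrowing (min) | Net power | Equivalent women per arm |
|---|---|---|---|---|---|
| 0 | 1.859 | 3.64 | −1.8 | 89.8% | −2.3 |
| 0.02 | 1.840 | 3.61 | 0.4 | 90.3% | 0.5 |
| 0.05 | 1.812 | 3.55 | 3.7 | 91.2% | 5 |
| 0.10 | 1.763 | 3.46 | 9.4 | 92.5% | 13 |

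The last column is 143/[(1 − R2) × 426/419] − 143. Break-even is R2 = 7/426 = 0.016.

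**3. Is that range plausible?** A binary factor with share p and effect d hours gives R2 = p(1 − p)d²/324. Assume unscheduled Cesarean in 10% to 20% of women. At the plan's 12 h ceiling, R2 is 0.04 to 0.07; at 6 h it is 0.01 to 0.02. One listed factor could therefore clear the break-even or only just reach it.

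**4. Strata alone.** Suppose the stratum is site (an assumption), with shares from 50/50 to 80/20.

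- Objective 1, assumed gap of 3 to 6 h: R2 0.004 to 0.028, power 90.4% to 91.0%, a gain of under 1 point.
- Objective 2, assumed gap of 10 to 20 percentage points: the binomial variance falls by share × (1 − share) × gap², for example 0.5 × 0.5 × 0.20² = 0.01. Power becomes 81.6% to 82.9%, against 81.3%.

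**5. Direction of any error.** If strata explaining R2 are ignored, the one-sided error is about 1 − Φ(1.96/√(1 − R2)). That is 2.4%, 2.2% and 1.9% at R2 0.02, 0.05 and 0.10, all below the nominal 2.5%.

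**The case against.** An unadjusted primary analysis with adjusted sensitivity analyses is a legitimate and common choice. Readers will see adjusted estimates anyway; only the deciding one would change. The benefit rests on an R2 and a site effect that the documents do not supply. At R2 0.02 the net gain is 0.1 point, and at zero it is a loss. Naming the strata takes one line, whereas a seven-covariate model with a missing-data rule is a larger change for roughly 0 to 2 points. All of this stands, and it is why the point is offered as an improvement.

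Three stronger readings are tempting, and the documents do not support them.

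- **That ignoring the strata makes the analysis invalid or too liberal.** Step 5 shows the opposite direction, and the effect is slight.
- **That the plan fails to define its strata.** Some front pages were not available, and a separate randomisation document may name them. What can be said is that the available text does not.
- **That the intervention-versus-placebo contrast is in danger because "we will have 80% power for the noninferiority analysis comparing these two groups".** The plan labels this a sensitivity analysis, so it decides nothing. Net of seven covariates its power would be 80.3%, 81.5% or 83.5% at the three R2 values, against 80.5% now, so at 0.02 adjustment slightly costs power.

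What survives is that the randomisation and the deciding analyses do not match, and that aligning them, with factors the plan already lists, is inexpensive.

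**Conclusion.** The point holds as a modest, optional gain. Nothing in V.E is wrong as written and the sample size stands. If strata and seven pre-allocation covariates explain 5% to 10% of the variance, Objective 1 gains about 1 to 2.3 points of power and its interval narrows by about 4 to 9 minutes each side. At 2% the gain is negligible. If they explain nothing, just under half a point is lost (90.2% to 89.8%). For Objective 2, using the strata gains about 0.3 to 1.6 points if they are sites with the gaps assumed. These sizes rest on assumed R2 values and site gaps. The mismatch between randomisation and analysis rests on the text alone.

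**What to change.** 1. **Use the strata.** Name the randomisation factors and include them in both main analyses. For Objective 1, use a linear model for the mean difference, still judged against 6 hours. For Objective 2, use a Mantel-Haenszel or standardised risk difference; the odds ratio from a logistic regression is conditional and not on the planned scale.
2. **Fix a short covariate list for Objective 1**, taken from V.E and limited to factors set before allocation: infant sex, age, primiparity, pre-pregnancy BMI, unscheduled Cesarean, diabetes and hypertension. Add stress and feeding intention only if they are confirmed as recorded before allocation. The documents do not state the order of questionnaire and injection.
3. **State a missing-covariate rule** so that no randomised woman is dropped, for example overall-mean imputation for BMI and a not-recorded category for binary factors.
4. **Fix both models before any comparative outcome summary by arm is produced.** The lock must refer to such summaries and not to individual outcomes, because "no one will be blinded as to assignment to the open control arm". If summaries by arm have already been seen, keep the unadjusted analyses as primary.
5. **Otherwise keep the unadjusted interval and chi-squared test as sensitivity analyses.**

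The cost is protocol and SAP wording, export of the stratum variable from REDCap, the missing-covariate rule, and 8 of 427 degrees of freedom with one two-level stratum. The seven covariates are already listed in the plan.

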## **II. Study Summary**

**We will conduct a randomized controlled trial (RCT) to evaluate the effects of immediate postpartum initiation of DMPA on breastfeeding and long-term contraceptive use.** We will enroll approximately 800 adult women who have delivered a healthy, full-term infant at a participating hospital, who intend to breastfeed for  $\geq 6$  months, and who want to use DMPA (Depo-Provera; Pfizer Corp.) We will randomize women to **receive within 48 hours of delivery: 1) DMPA (“intervention” arm), 2) placebo injection (“placebo” arm) or 3) no injection (“open control” arm).** The first two arms will be blinded while the open control arm will be unblinded. Note that postpartum patients at the study site do not receive DMPA before discharge as standard care. At enrollment, women will receive condom counseling and provision and referral for contraception at 12 weeks (intervention and placebo arms) or at 6 weeks postpartum (open control arm). We will collect data on lactogenesis, infant feeding and growth, and contraception use during 12 follow-up months. We conducted a pilot study (N=100) in the target population at OSU, which supports the feasibility of the current trial.

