#### IV. Literature

##### A. Literature in Support of Objective 1: The relationship between immediate postpartum initiation of DMPA and lactation.

Because delayed lactogenesis stage II is associated with a range of poor breastfeeding outcomes (failure to initiate, reduced duration, and use of supplements), identifying any negative effect of progestin on lactogenesis would be important. In theory, progestin could inhibit the process. Production of progesterone by the adrenal glands, ovaries and placenta increases during pregnancy. Plasma progesterone levels do not decrease until after delivery of the placenta, after which time, levels decline rapidly, reaching follicular phase levels after 2-3 days. This decline, along with decreased estrogen levels and infant suckling, is thought to trigger lactogenesis. Cases of placental retention, in which lactogenesis has been delayed up to three weeks, support this physiologic mechanism. Also, exogenous progesterone given around the expected parturition time in rats or after fetus removal in ewes inhibits milk secretion; in contrast, no inhibitory effect occurred in rat models when progesterone was given after the establishment of lactation. Note, though, that progesterone and the synthetic progestogen, medroxyprogesterone acetate, used in the contraceptive injectable are different compounds, which are known to produce different effects in women; thus, **findings from trials on progesterone use in animals are suggestive but cannot be assumed to represent the effects of DMPA use in women.**

**A recent systematic review found no RCTs in humans on the effect of immediate postpartum initiation of DMPA on lactation.** Three RCTs compared immediate postpartum use of a progestin-only method other than DMPA with the initiation of the same or a different hormonal method later during the puerperium. The three trials made the following comparisons: etonogestrel implant used immediately postpartum versus DMPA at 6 weeks postpartum;

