**Table 1. Data collection by objective, location, schedule and mode of collection, and compensation.**

Objective	Data collection	Location	Schedule and mode of collection	Compensation
1,2	Enrollment Questionnaire	Participating hospital	Self-administered within 48 hrs of delivery	\$80 in cash at OSUWMC; \$80 in electronic gift card at Emory-affiliated Hospital
1	Milk Let-Down Questionnaire	Participating Hospital / text, telephone, email	Interviewer administered ≤3 times daily in person at OSUWMC or Emory-affiliated hospital, then daily via text, telephone or email during the first 7 days postpartum until lactogenesis stage II occurs	One payment of \$30 in electronic gift card at all sites
1,2	Follow-up Questionnaire	Online	Self-administered at 1, 2, 4, 6, 9 and 12 months. Questionnaires at 1, 6 and 12 months include infant anthropometric measures* from well-child visit data	\$10 per interview in electronic gift card at all sites
1	Infant adiposity (PEA POD) and other infant measures*†	OSUWMC only	Measured by trained study staff at 4 months of age	\$40 in gift card, a branded gift (e.g., a cell phone popsocket or a pen with light) worth less than \$4.00, and either parking pass or transportation by cab to appointment

OSUWMC = Ohio State University Wexner Medical Center; \*Includes weight, length, head circumference; †Visit not completed by participants who delivered at an Emory-affiliated Hospital

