## B. Study Population

We will enroll a convenience sample of 800 women. Women can enroll either prenatally or postpartum before their hospital discharge.

To enroll prenatally, women need to meet the following eligibility criteria:

- 1) Intend to deliver in the Labor and Delivery Unit at a participating ;
- 2) Are ≥18 years of age;
- 3) Speak English;
- 4) Intend to breastfeed, or express milk for their infant, for ≥6 months;
- 5) Do not want to become pregnant within the first 12 months after delivery;
- 6) Want to start use of DMPA immediately after delivery before discharge; **AND**

- 7) Intend to reside in Ohio for those who deliver at OSUWMC or intend to reside in Georgia for who deliver at an Emory-affiliated Hospital for the first 12 months after delivery.

Women will be excluded if they have any contraindications to DMPA (per package insert), which consist of the following:

- 8) Undiagnosed vaginal bleeding;
- 9) Known or suspected malignancy of breast;
- 10) Active thrombophlebitis, or current or past history of thromboembolic disorders, or cerebral vascular disease;
- 11) Liver dysfunction or disease; **OR**
- 12) Known hypersensitivity to Depo-Provera.

Women who enroll prenatally will need to rescreen following delivery to confirm their eligibility. Women enrolling after delivery or who are rescreening will need to meet criteria 2-12 above as well as the following eligibility criteria:

- 1) Are a postpartum patient in the Labor and Delivery Unit at OSUWMC or participating Emory-affiliated Hospital; **AND**
- 2) Have delivered a term, singleton infant of  $\geq 2500$  grams without any apparent health concerns.

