### C. Outcome Measures

The primary outcome is time to lactogenesis stage II measured with participant reports. Chapman and Perez-Escamilla validated the accuracy of maternal perceptions of the timing of lactogenesis stage II, and we will adhere to their questions and methods. Immediately after enrollment, we will record whether women perceived that their milk “has come in” and, if so, we will capture this event to the estimated post-delivery hour. Participants will be re-asked (up to 3 times daily in person during their hospital stay and then daily via their choice of text, telephone, or email after discharge) during the first 7 days postpartum until the event occurs.

Secondary outcomes include 1) length of breastfeeding continuation, which has been negatively associated with both experiencing a delay in lactogenesis stage II and maternal perception of the adequacy of her milk production; 2) perceived need for supplementation (any and timing); and 3) use of supplementation (any and timing). We will use established questions on breastfeeding (any and exclusive feeding) from the National Immunization Survey, which also are used on the Health and Nutrition Examination Survey (NHANES).

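### Breastfeeding duration is assigned only t-tests or chi-squared tests, with no rule for women still breastfeeding at 12 months or lost while breastfeeding

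*Combined protocol and SAP*

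**What the plan says.** Section V.C (Outcome Measures) lists length of breastfeeding continuation as a secondary outcome, followed by "perceived need for supplementation (any and timing); and 3) use of supplementation (any and timing"). Section V.E (Analysis of Objective 1) names breastfeeding duration and states that "a traditional superiority analysis will be conducted (test for significant differences using t-tests or chi-squared tests as appropriate"). It adds: "We will report two-sided 95% CIs for all outcomes so that post-hoc noninferiority analyses could be conducted".

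Three design features bear on whether durations will be complete:
- Follow-up has a fixed end. Section II says: "We will collect data on lactogenesis, infant feeding and growth, and contraception use during 12 follow-up months". Table 1 gives the questionnaire schedule: "Self-administered at 1, 2, 4, 6, 9 and 12 months".
- Eligibility (section V.B) requires that women "Intend to breastfeed, or express milk for their infant, for ≥6 months", with no upper limit.
- The sample-size text assumes 20% attrition at 12 months. That figure is given for Objective 2.

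Section V.E plans multiple imputation, under missing-at-random and missing-not-at-random assumptions, for two places only. One is the primary outcome ("although we expect only a negligible amount of missing data for the primary outcome"). The other is contraception use at 12 months, with DMPA use analysed similarly. Section VIII (Internal Validity) warns that attrition differing by arm could bias breastfeeding duration, and gives this as a reason for not making duration primary.

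No section mentions censoring, Kaplan-Meier, log-rank or Cox methods, or a visit at which continuation would be made binary.

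**The concern.** A t-test on duration cannot be run until every woman has a number. For a woman still breastfeeding at month 12, or lost while breastfeeding, the plan does not say what that number is. An analyst could:
- take the last contact as the stop;
- cap at 12 months and omit women lost while breastfeeding;
- cap at 12 months and use only women followed to the end;
- run a chi-squared test on continuation at some visit.

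The words 'as appropriate' choose between two tests. They settle neither the coding nor the visit.

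Objective 1 asks whether early DMPA harms breastfeeding, and section III says the secondary outcomes are there to make a negative effect easier to detect. A coding that pulls the difference towards zero errs towards finding no harm. The confidence intervals offered for later noninferiority reading carry the same open choice.

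**Working it through.** **Inputs from the documents.** 143 women per arm; intervention vs the other two arms combined (143 vs 286); two-sided 0.05; 12 months of follow-up with questionnaires at 1, 2, 4, 6, 9 and 12 months; 20% attrition (114 + 228 = 342 of 429 remain, so 87 are lost). The Background cites a U.S. study in which almost one-third of women intending to breastfeed did not start or stopped within 6 weeks.

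**Assumptions.** The primary comparison's grouping also applies to duration. Durations are exponential. Loss time is uniform over 0-12 months and independent of stopping. A stop is known, with its exact date, if it precedes the last completed questionnaire.

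**1. The plan's own figure.** None is given for duration. For the primary outcome, SE = 18 × √(1/143 + 1/286) = 1.844 h, and power = Φ(6/1.844 − 1.960) = Φ(1.295) = 90.2%, against 90% stated. This confirms the 143 vs 286 comparison used below.

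**2. True difference.** With median m, the mean duration restricted to t months is R(m,t) = (m/ln 2)(1 − 2^(−t/m)).
- R(6,12) = 8.656 × 0.750 = 6.49, with 25% still breastfeeding at month 12.
- R(8,12) = 11.542 × 0.646 = 7.46, with 35% still breastfeeding.
- Difference: −0.97 months.

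**3. Last-contact coding, equal 20% loss.** A lost woman's last completed questionnaire is at 0 (none), 1, 2, 4, 6 or 9 months, with probabilities 1/12, 1/12, 2/12, 2/12, 3/12 and 3/12. Averaging R(m,v) over these gives G(6) = 3.39 and G(8) = 3.68. The mean recorded duration is 0.8 × R(m,12) + 0.2 × G(m):
- median 6: 0.8 × 6.492 + 0.2 × 3.391 = 5.87
- median 8: 0.8 × 7.461 + 0.2 × 3.681 = 6.71
- difference: −0.83 months, about 14% smaller than the true value.

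**4. Power in the same case** (simulation, 20,000 trials; repeat runs agree within about 2 points).
- Last contact: 48%.
- Capped, omitting women lost while breastfeeding: 53%.
- Capped, completers only: 50%.
- Kaplan-Meier restricted mean: 57%.
- Log-rank: 62% (exponential durations favour it).

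The three t-test codings disagree on significance in about 18% of trials.

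**5. No effect, equal loss.** At medians of 7 and 7 months with 20% loss, each coding alone rejects about 5%. The most favourable of the three rejects about 8%.

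**6. No effect, loss of 25% vs 15% (assumed).** The last-contact error is (0.25 − 0.15) × [R(m,12) − G(m)].
- Median 7: 0.10 × (7.02 − 3.55) = 0.35 months; simulated rejection 12%.
- Median 2.4: 0.10 × (3.35 − 2.23) = 0.11 months; simulated rejection 6-7%.

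At a median of 7, the coding that omits women lost while breastfeeding is off by 0.19 months and rejects 7%. Completers only, the restricted mean and log-rank stay at 5%.

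The 2.4-month median is an exponential fit to the Background's one-third by 6 weeks (1.38 months): m = 1.38 × ln 2 / ln 1.5 = 2.36. It leaves about 3% breastfeeding at month 12.

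**The case against.** Much of the opposing case stands.

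**Few durations might be censored.** The early stopping cited in the Background points that way, and a woman who stopped before being lost has a known duration. Women intending at least 6 months may last longer than that study's group, but the short end of the range must be shown, and there the bias is small.

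**Unequal loss is not established.** Section V.E sees no reason to expect it for contraception use. Section VIII raises it for duration only as a conditional. The 25% vs 15% split is an assumption.

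**Each coding, fixed in advance, holds 5% under equal loss.** A stated cap rule within the planned t-test would remove the open choice, and completers-only coding also held 5% under the unequal loss tested. A cap rule would still leave women lost while breastfeeding to be dropped or imputed.

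**Three stronger readings are tempting but not supported.**
- A reader might argue for a particular test because the literature section reports that "no inhibitory effect occurred in rat models when progesterone was given after the establishment of lactation", suggesting an early-only effect. The same section cautions against carrying animal findings over to DMPA in women. It also describes a levonorgestrel IUD trial with the opposite pattern: no difference at 6-8 weeks, less continuation at 6 months.
- Adding a 12-month chi-squared test to the three t-tests raises the disagreement rate well above 18%. That compares a proportion with mean durations, which are different quantities, and the plan does not select month 12 for duration.
- Supplementation timing looks like the same problem. It falls under the analysis sentence only by implication, was not simulated, and needs its own rule for women who stop breastfeeding first.

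**Conclusion.** The gap is real and needs no simulation to see: a time outcome with a fixed end of follow-up and expected attrition is given tests that cannot use incomplete durations, with no coding rule and no missing-data analysis.

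Its size is uncertain. Under the assumptions above, the t-test codings have about 47-53% power against 57% for the restricted mean at medians of 6 vs 8 months. The possible bias under 25% vs 15% loss runs from about 0.1 to 0.35 months, according to how long women breastfeed.

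A reader might infer that the trial's main conclusion is at risk. It is not: time to lactogenesis II and the sample size do not depend on duration. The plan sets no margin for duration and labels noninferiority on it post hoc, so no confirmatory claim rests on it. This is a cheap improvement to a secondary analysis.

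**What to change.** In section V.E, Analysis of Objective 1:

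- Analyse breastfeeding duration (any and exclusive, separately) as time to event. Stopping is the event; censor at the last completed questionnaire or month 12.
- Report Kaplan-Meier curves and the 12-month restricted mean difference with 95% CI, which keeps the month scale of the planned comparison of means. Give a log-rank test as supportive. Do not rest the choice on the animal data.
- Extend the planned missing-at-random and missing-not-at-random sensitivity analyses to duration.
- If continuation is also analysed as binary, name the visit.
- Apply the same approach to time to supplementation only with a stated rule for women who stop breastfeeding before any supplementation event. Keep chi-squared tests for any supplementation.

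**Cost.** Wording and slightly more analysis work; the scheduled questionnaires already collect breastfeeding data. The method assumes non-informative censoring, which can fail. In a no-effect simulation where women in one arm only were three times as likely to drop out at the questionnaire after stopping (loss 18% vs 15%), the restricted mean was off by +0.17 months and rejected 7%, against +0.09 and 5-6% for the capped t-tests. The missing-not-at-random analysis is there to check this.
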